Interim analyses. We will conduct interim analyses to assess efficacy (rejecting null) and futility (rejecting alternative) at each 25% of the maximum enrollment using a group sequential procedure. Specifically, a gamma spending function will be used with parameters -4 and -2 for efficacy and futility, respectively.¹⁰⁵ Thus, boundaries at the 1st through 4th analyses for efficacy (futility in parentheses) will be P \leq 0.0016 (P>0.9572), P \leq 0.0048 (P>0.7186), P \leq 0.0147 (P>0.2389) and P \leq 0.0440 (P>0.0440), Figures 7 and 8.

Figure 7. Boundaries for efficacy and futility.

Figure 8. Alpha and beta spending functions

Type I error. We will use a parallel gatekeeping procedure to control the study-wide type I error at 0.05.¹⁰⁶ For this procedure we therefore a priori prioritize the study outcomes into ordered sets, as Aim 1, Aim 2a, Aim 2b and then Aim 2c. Analysis will proceed in that order, and testing will proceed through each "gate" to the next set if and only if at least one outcome in the current set reaches significance. The significance level for each set will be 0.05 times a cumulative penalty for non-significant results in previous sets (i.e., a "rejection gain factor" equal to the cumulative product of the proportion of significant tests across the preceding sets). Within a set, a multiple comparison procedure (Bonferroni correction) will be used as appropriate to control the type I error at the appropriate level. SAS statistical software (Carey, North Carolina), R programming language (The R Project for Statistical Computing) and East 5.3 software (Cytel Inc.) will be used for all analyses.

Sample size considerations. Our sample size estimate is based on the primary specific aim of whether the addition of an ambulatory CPNB decreases phantom limb pain intensity resulting from a traumatic amputation compared with current standard-of-care treatment at 4 weeks following the ambulatory CPNB. Receiver operating characteristic curve analyses demonstrate that changes from baseline of at least 1.7 along a 10-point NRS accurately identified patients who rated improvements as "much improved" or more, compared with those who perceived no change or worsening following analgesic interventions.⁸⁸ Multiple additional studies confirm this degree of reduction as clinically meaningful to individual patients with chronic pain.^{85,107,108}

Therefore, we power our study to be able to detect group differences in mean change from baseline of 1.7 points or more on the NRS. Based on a conservative standard deviation estimate for each group of 3.0 at 28 days, a correlation of 0.50 between baseline and follow-up NRS, a two-sided test at the 0.05 significance level, power of 0.90, and 4 equally spaced analyses (3 interim and 1 final, as needed), a maximum of 72 subjects in each group (N=144 total) is required (East 5.3 software, Cytel Inc). The expected sample size for this group sequential design (i.e., average sample size over thousands of such trials, stopping when a boundary is crossed) is a total of 100 under the alternative and 102 under the null hypotheses. Table 2 reports boundary crossing probabilities at each of the 4 analyses for this design, assuming that either the null or alternative hypotheses were true. For example, there is a cumulative 8%, 37% and 75% chance of crossing a boundary at the 1st, 2nd, and 3rd analyses, respectively, if the alternative hypothesis were true. However, if the true standard deviation at 28 days were smaller, say 2.5 instead of 3.0, then the cumulative probability of stopping for efficacy at the 1st, 2nd and 3rd analyses, respectively, would increase to 16%, 55% and 88% under the alternative hypothesis.

Fraction of Maximun Accrual		Cumulative Accrual	Alpha Spent	Beta Spent	P-value Bo	oundaries	Boundary Crossing Probabilities		
					HO	H1	Under H0	Under H1	
0.250		36	0.002	0.010	0.0016	0.9572	0.044	0.083	
0.500		72	0.006	0.027	0.0048	0.7186	0.269	0.290	
0.750		108	0.018	0.054	0.0147	0.2389	0.485	0.379	
1.000		144	0.050	0.100	0.0440	0.0440	0.202	0.248	

 Table 2. P-value boundaries and boundary crossing probabilities for group sequential design.

10. HUMAN SUBJECTS

Inclusion criteria: Adults of at least 18 years of age, (1) with an upper or lower limb traumatic or surgical amputation at least 12 weeks prior to enrollment distal to the mid-humerus or hip (femoral head remaining), respectively, and including at least one metacarpal or metatarsal bone, respectively; (2) who experience at least moderate phantom limb pain—defined as a 2 or higher on the Numeric Rating Scale (NRS; 0-10, 0= no pain; 10=worst imaginable pain)—at least 3 times each week for the previous 8 weeks in a single limb (in the case of multiple amputations); (3) accepting of an ambulatory perineural infusion for 6 days; (4) willing to avoid changes to their analgesic regimen as well as elective surgical procedures from 4 weeks prior to and at least 4 weeks following the initial catheter placement (preferably 4 weeks following the optional second/crossover catheter insertion as well); and (5) have a "caretaker" who will transport the subject home following the catheter insertion(s), and remain with the subject for the first night of the infusion(s).

Exclusion criteria. (1) Known renal insufficiency (creatinine > 1.5 mg/dL); (2) allergy to the study medications; (3) pregnancy; (4) incarceration; (5) inability to communicate with the investigators; (6) morbid obesity (body mass index > 40 kg/m²); (7) comorbidity that results in moderate-to-severe functional limitation (American Society of Anesthesiologists physical status classification > 2);⁶⁶ and (8) possessing any contraindication to ambulatory perineural catheter placement or perineural local anesthetic infusion, such as a current infection at the catheter insertion site, immune-compromised status of any etiology, uncontrolled anxiety/panic disorder, inability to contact the investigators during the perineural infusion (e.g., lack of telephone access). Of note, multiple amputations and phantom limb pain in more than one location are not exclusion criteria. Due to the increased explosive power of modern armaments, multiple-amputation casualties are now a frequent occurrence within the U.S. military. It is therefore vitally important to assess the effectiveness of ambulatory continuous peripheral nerve blocks on phantom pain for this patient population.

There are no restrictions on race, ethnicity, or sex; and, individuals of all races, ethnicity, socio-economic status, and sex are of interest and will be enrolled. We anticipate a very diverse subject pool that generally represents the demographics of the population of the United States given the wide-variety of recruitment sites: military, Veteran, and civilian; the East, Midwest and West coasts; private, State supported, and Federally supported; as well as academic and nonacademic. Adult subjects (18 years and older) will be enrolled. There will be no participants from vulnerable populations, such as pregnant women, children, or prisoners. The enrollment goal for this study is 144 subjects evaluable subjects with measured primary endpoints distributed over the five enrolling centers. Therefore, to allow for drop-outs and other unevaluable subjects, we anticipate enrolling a total of 180 subjects over the five enrolling centers, and 60 subjects specifically at UC San Diego.

11. RECRUITMENT

Potential study subjects will be introduced to the proposed investigation by one of their healthcare providers, receive a letter from the investigators (subjects within amputee databases), or view an advertisement in clinic, a support group, print publication, or website. They will contact either a research coordinator or site director for additional details on the study. This will include the study inclusion and exclusion criteria. Subjects will be asked to contact the study coordinator or site director again with further questions or to request enrollment (subjects can request enrollment during the first phone contact, but they will not be asked to enroll at that time to avoid any perceived "pressure" to enroll). If a subject desires enrollment, the study coordinator will schedule a catheter-insertion appointment at the enrolling center.

Of note, various hospitals are planning in the future on sending out information regarding this study to their own patients who previously underwent limb amputations. These hospitals will request IRB approval from their own IRBs to participate in this way. The reason that these hospitals will need to obtain their IRBs' approval is because they want to extract from their own databases the names and addresses of their previous patients who received an amputation at their own hospital; and, then send these individuals information regarding the multicenter study on phantom limb pain being overseen by UCSD. Potential subjects who are interested in participating will contact the UCSD P.I. (myself) or another IRB-approved UCSD investigator/coordinator for further information and screening. Any subjects who desire participation and fit all criteria will be enrolled at one of the four currently-IRB-approved enrolling institutions for this multicenter study.

So, these external hospitals' involvement will be to simply produce the mailing labels for their previous amputation patients, and affix these labels to pre-stamped envelopes containing IRB-approved (both UCSD and other IRBs) study information. Once mailing these envelopes, the external hospitals' IRBs will be closed, as they will have nothing further to do with the study. They are involved in no enrollment, treatment, data collection, or data analysis. They are simply querying their database for patients and then producing address labels (affixing these labels to envelopes and dropping them all in the U.S. mail).

These institutions include:

12. INFORMED CONSENT

If a patient desires study participation, written, informed consent will be obtained (either at that time in clinic if seen in person, or upon presentation for catheter placement but prior to all interventions and outcome measurements). An investigator or research coordinator specifically trained in both study details and appropriate consenting procedures will attain verbal and written informed subject consent. The method of documenting consent will be using written informed consent forms approved by the IRB.

13. ALTERNATIVES TO STUDY PARTICIPATION

Patients can decline enrollment. If they do so, they will still receive their current analgesics.

14. POTENTIAL RISKS

- 1. Infection. Since the catheter will be left in place for 6 days, there is a very small risk (<1%) of infection.
- 2. Falling. The risk of falling due to the perineural infusion in lower extremity amputees is currently unknown, since this intervention has not been prospectively investigated previously.
- 3. Catheter dislodgement. There is a risk of the catheter being accidentally and prematurely dislodged or becoming disconnected from the infusion pump.
- 4. Catheter retention (<0.01%)
- 5. Bleeding (<0.01%)
- 6. Nerve injury (<0.01%)
- 7. Local anesthetic toxicity (<0.01%)
- 8. Loss of confidentiality

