amputation will be provided with crutches that they will be instructed to use until the day following catheter removal. Bathing will be permitted, as long as the catheter and infusion pump remain dry (e.g., sponge baths). Subjects will be discharged home with their portable infusion pump and perineural catheter *in situ*, and telephoned beginning the afternoon of catheter insertion and each subsequent day until catheter removal. During these calls, investigators will review gross sensory and motor function of the remaining limb; local anesthetic toxicity symptoms; infections signs and symptoms; catheter site appearance; infusion pump functioning (simply the volume infused displayed continuously and a flashing green light); and answer any questions.

With thorough catheter securing techniques such as catheter tunneling and others included in this protocol, the catheter dislodgement rate is less than 5% for infusions greater than one week, in both civilian⁷⁷ and military settings.⁶ However, inadvertent premature catheter dislodgement does rarely occur.³⁷ In the proposed study, if premature dislodgement occurs, the subject may opt to have the catheter replaced as soon as can be arranged with the investigators. All subjects will be retained in their respective treatment groups for analysis per the intent to treat principle.

Six days following catheter insertion, the study fluid reservoir(s) will be exhausted and subjects or their caretakers will remove the perineural catheter(s) with instructions given by an investigator *via* telephone. This procedure encompasses simply removing the occlusive dressing and gently pulling on the exposed perineural catheter. Home removal has been used successfully for tens-of-thousands of previous patients,^{31,37} and in one survey over 95% of patients responded that catheter removal was "easy" and that they would not have preferred to return for removal.³² However, if a subject desires, the patient may return to the medical center for catheter removal by a health-care provider.

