15. RISK MANAGEMENT PROCEDURES AND ADEQUACY OF RESOURCES

Planned procedures for protecting against or minimizing potential risks include:

During catheter placement, subjects will be continuously monitored with pulse oximetry, noninvasive blood pressure cuffs, and EKG (standard for catheter placement). Subjects will receive an IV so that emergency medications could be given, if needed. As described above, catheters will be placed under sterile conditions as is standard-of-care for any percutaneous catheter placement.

During the infusions, the subjects will be contacted through the day following catheter removal by an investigator or research coordinator, and subjects will have a physicians' pager and cellular phone numbers available to respond 24 hours/day and 7 days/week until the day following catheter removal. This procedure has proven effective for ambulatory surgical patients with perineural local anesthetic infusions. Patients will be called daily and asked about signs and symptoms of catheter infection. Should a catheter become infected, the catheter will be removed and oral antibiotics prescribed. Subjects with lower extremity infusions will be given crutches to use during the infusion itself.

If a catheter is accidentally and prematurely dislodged or disconnected from the infusion pump, the patient will turn off the infusion pump and may opt to have the catheter/pump replaced as soon as possible with the investigators.

The risks to confidentiality are the release of names/ telephone numbers/ demographic data (e.g. weight, age,

height), which will be minimized by the use of password-protected computers and case report forms that will be stored in locked offices. The study is triple-masked and placebo-controlled, so in case of a complication related to the delivery of study fluid, the investigational pharmacy will be contacted to determine study group. However, in case of a severe adverse event or medical emergency, the pump can be disabled, the tubing clamped shut, and/or the catheter removed—so that infusion may be stopped without knowing study group assignment.

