Subjects will be given clear instructions to call an investigator with any questions or concerns regarding their study participation. If a patient experiences an injury that is directly caused by this study, only professional medical care that they receive at the medical center. No other compensation is offered. Any adverse events will be reported to the IRB using the standard adverse events reporting and upon continuing review (depending on severity, as defined by the IRB).

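### Fall risk in lower-limb amputees is declared unknown, but the listed daily call content does not prompt for falls, so non-injurious falls may go unrecorded

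*Combined protocol and SAP*

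**What the plan says.** Section 14 lists falling second among eight risks and says that "The risk of falling due to the perineural infusion in lower extremity amputees is currently unknown", giving as the reason that the intervention has not been studied prospectively.

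Two places describe the daily calls. Section 9 (Ambulatory infusion) gives the topics as "gross sensory and motor function of the remaining limb; local anesthetic toxicity symptoms; infections signs and symptoms; catheter site appearance; infusion pump functioning", together with time for the subject's own questions. Section 15 says "Patients will be called daily and asked about signs and symptoms of catheter infection". On duration, section 9 runs the calls until catheter removal, while section 15 says "the subjects will be contacted through the day following catheter removal".

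Several protections are in place. Lower-limb subjects are "provided with crutches that they will be instructed to use until the day following catheter removal" (section 9). A caretaker must stay for the first night (section 10). A physician can be reached around the clock, and subjects are told to call with concerns (section 15). On reporting, section 15 says "Any adverse events will be reported to the IRB using the standard adverse events reporting and upon continuing review", with the route or extent varying by severity under the IRB's definition. The medical monitor and the DSMB review adverse events every one and six months respectively (section 9, Study Design).

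Neither Table 1 nor the questionnaire text in section 9 contains a fall item. The Statistical Plan and Data Analysis part of section 9 describes no summary of adverse events of any kind.

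**The concern.** Falling is the one listed risk whose size the plan declares unknown, and this trial is a prospective study in which it could be observed. The calls that could record it already take place every day. As listed, they prompt for infection and local anesthetic toxicity, which section 14 puts below 1% and below 0.01%, but not for falls.

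If callers follow the listed content exactly, a fall that causes no injury depends on the subject raising it. A low or zero count would then be hard to tell from incomplete recording. What is at stake is the completeness of the safety information reaching the medical monitor, the DSMB and the final report. It bears on section 18, which treats infection as the largest risk and judges the risks minimal relative to the benefits. It does not bear on the pain outcomes.

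**Working it through.** **Step 1: stated risks against listed call content.** The plan gives no fall rate, fall endpoint or fall-based sample size, so there is no figure of its own to reproduce. The check is a comparison of sections.

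| Risk (section 14) | Stated size | Listed call content that bears on it (sections 9, 15) |
|---|---|---|
| Infection | <1% | Infection signs and symptoms; catheter site |
| Falling, lower limb | unknown | None named; motor-function review could bring a fall out incidentally |
| Dislodgement | no figure in section 14; section 9 cites under 5% | Catheter site; pump functioning |
| Nerve injury | <0.01% | Sensory and motor function |
| Local anesthetic toxicity | <0.01% | Toxicity symptoms |

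**Step 2: do the other provisions count falls?** Crutches and the first-night caretaker help prevent falls or may observe one, but neither is a recording procedure. Telephone access relies on the subject to call. IRB reporting and review by the medical monitor and DSMB act on events that have been recorded. These routes would probably bring injurious falls to light. Non-injurious falls have no prompted route in the text.

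**Step 3: exposure.** Lower-limb subjects receive 2.5 mL/h (femoral) plus 5 mL/h (popliteal-sciatic), or 7.5 mL/h in total. A volume of 1,100 mL lasts 1,100 / 7.5 = 146.7 h, about 6.1 days, at home. The optional crossover repeats this.

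**Step 4: what the two arms share.** Every lower-limb subject receives 20 mL of 2% lidocaine through each catheter before randomization (section 9, Lower extremity amputation). For the first hours both arms therefore have a nerve block, and a fall then does not reflect the study infusion.

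**Step 5: what a zero count could mean if falls were fully recorded.** For 0 falls in n subjects, the one-sided 95% upper bound is 1 − 0.05^(1/n). The lower-limb share is not given, so 50% to 100% is assumed. Total sizes come from sections 9 and 10.

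| Total N | Per arm | Lower-limb n per arm | Upper bound |
|---|---|---|---|
| 100 (expected) | 50 | 25 to 50 | 11.3% to 5.8% |
| 144 (maximum) | 72 | 36 to 72 | 8.0% to 4.1% |
| 180 (enrolled) | 90 | 45 to 90 | 6.4% to 3.3% |

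For example, with n = 36, 1 − 0.05^(1/36) = 0.080. The 180 row is an upper limit on n, since some enrolled subjects may not be infused. The bounds apply only if falls are fully recorded. They show what the trial could contribute and do not estimate what would be missed.

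**The case against.** The strongest objection is that the finding rests on silence in a summary. Section 9 gives one sentence of call topics. The call form and case report forms are not in the document and may already contain a fall item. This stands, and it is why the first step of the fix is to check.

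A second objection is that the risk is recognised and managed, through open disclosure, crutches, a caretaker, daily contact, motor-function review, round-the-clock access and independent oversight. This also stands. It narrows the gap to non-injurious falls that the subject does not mention, but it does not close it, because none of these measures is described as asking about falls.

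Third, estimating a fall rate is not among the specific aims in section 6. That is true, but monitoring a risk the plan lists itself needs no efficacy aim. The broader omission is arguably the absence of any adverse event summary. Falls are singled out here because theirs is the only risk declared unknown.

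Fourth, saline is not a block-free reference throughout, because of the lidocaine given before randomization. This is correct and limits any reading of falls in the first hours.

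A reader might infer that the trial does not capture falls at all, or that subjects are unprotected. The document supports neither, given the reporting routes and precautions in sections 9, 10 and 15. A reader might also infer a known degree of under-counting, but the document gives no reporting fraction.

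**Conclusion.** The point holds in a narrow form. The risk is stated as unknown, the listed call content does not prompt for it, and non-injurious falls during the infusion may therefore go unrecorded, leaving the medical monitor and DSMB with an incomplete count. This is a low-priority, inexpensive safety improvement, held with moderate confidence because the call form is unseen.

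The shortfall cannot be sized from the document. The zero-count bounds (8.0% to 4.1% at the maximum of 72 per arm) rest on an assumed lower-limb share and full recording. The efficacy analysis, type I error and sample size are unaffected. It would be wrong to read this as a demonstrated failure of safety monitoring, or as grounds for a formal comparison of fall rates between arms.

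**What to change.** 1. Confirm whether the daily call form already has a fall item.
2. If not, add one prompted question to each daily call: any fall since the last call, and any injury from it. Ask it through the day after catheter removal, in both infusion periods. This matches the contact period in section 15 and the crutch period in section 9.
3. Record the time of each fall relative to the lidocaine bolus, so that falls in the first hours can be identified.
4. Report fall counts among infused lower-limb subjects by arm for the initial infusion, descriptively and with exact confidence intervals. List crossover-period falls separately. Supply the counts to the medical monitor and DSMB, keeping to the plan's masking arrangements, and include them in the final results.

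The cost is one question on calls already made, one case report form line (with the time of the fall) and one descriptive table. No visits, staff or hypothesis tests are added.
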